5.5 Statistical Analysis

Measurement of serum C-peptide levels during MMTT and, specifically, the quotient of C-peptide (CP)/glucose (G) (ng/ml x100/mg/dl) at 90min during the test, have shown to be indicators of islet function and islet mass after allogeneic islet transplantation. Increments in the quotient according to islet mass (IEQ)/kg have also been identified. We expect this quotient to be applicable to the TPAIT setting in line with several studies showing that MMTT is a valuable assay to assess islet function after TPAIT. We applied the proposed increments to estimate levels of the CP/G (0.35±0.07) based on our historical TPAIT data, indicating on average IEQ/Kg infused of 4500±1000. Our hypothesis is that higher survival of beta cell mass due to the treatment will result in higher CP/G quotient in the HCQ-treated arm, compared to the placebo group, after normalization for IEQ/Kg infused. A one-sided, 2 sample t-test was used for sample size calculation with the assumption of equal variance between the two study arms. Assuming a 20-30% difference in outcome (CP/G quotient) between study arms, which is equivalent to 0.08-0.12 CP/G difference and a 0.07 standard deviation, a sample size of 6 subjects (1:1 randomization) will detect a CP/G difference of at least 0.12, assuming 80% power, with a 0.05 significance level. We propose that a sample size of 10 subjects (5 for each arm) with the same assumptions but at 75% power, (Table 2) will be justified, given the expected feasibility of subject enrollment and the pilot nature of this trial.

Table 3: Statistical Analysis

	Sample size (per arm)		
	Δ=0.08	Δ =0.1	Δ=0.12
SD=0.07	n=9	n=7	n=5
SD=0.08	n=12	n=8	n=6
SD=0.09	n=15	n=10	n=7

6. Adverse Events and Data Monitoring Committee (DMC)

7. Consent

Patients will be consented to participate in this study. Those whom agree to participate will be enrolled. A nurse coordinator whom performs the consent for TPIAT will perform the consenting process for this study. A copy of the consent form is attached to this IRB application.

8. Budget

An outline of our budget is found in table 4. Data collection and entry will be performed by the study's investigators at no cost. MMTT testing at 6 and 12 months post-TPAIT is part of the standard-of-care testing in all centers performing TPAIT and thus no additional resources will be allocated for MMTT conduction. The cost of the RNA genomic analysis will be covered by the [name] Laboratory at Stanford University School of Medicine at no additional cost to us.

An application will be submitted for the Research Program Committee (RPC) Grant to cover half of the study expenses (around \$11,000). The planned date of submission of the application is February 6th, 2017. The remainder of the budget will be covered internally from EMI funding and the study's PI.

Item	Units	Estimated expense of items	Total
	needed		expenses
HCQ (4 month supply) and Placebo (4 month supply)	600 HCQ pills, 600 matching placebo	 \$1,200 for capsule manufacturing \$1,750 onetime pharmacy initiation fee \$60 monthly drug storage and inventory maintenance fee 	\$1,200 \$1,750 \$240 \$1,600 \$2,452
		 \$40 dispensing fee per occasion \$2,452 for generic HCQ (#600) 	

Table 4: Preliminary proposed budget

Seahorse XF24 Islet Capture	2	\$369	\$738
Microplates from Agilent Technologies			
Islet controls from Lonza	11	\$945	\$10,395
Pharma&Biotech			
Genomic Analysis		\$0 (to be covered by [name]'s Lab)	\$0
MMTT testing		\$0 (to be covered by insurance	\$0
		providers)	
Expense of islet transport and care from		\$0 (to be covered by [name]'s Lab,	\$0
CCF to AGH, from AGH to both		AGH, and insurance providers)	
Stanford and CCF			
Statistical support		~\$2,000	~\$2,000
Data collection and entry		\$0 (to be performed by study	\$0
		investigators)	
			~\$20,375

9. Extramural Grant Application Plan

An application will be submitted for the Research Program Committee (RPC) Grant to cover the

remainder cost of the study. The planned date of submission of the application is February 6th, 2017.

10. References:

- 1. Johnston, P.C., et al., Factors associated with islet yield and insulin independence after total pancreatectomy and islet cell autotransplantation in patients with chronic pancreatitis utilizing off-site islet isolation: Cleveland Clinic experience. J Clin Endocrinol Metab, 2015. **100**(5): p. 1765-70.
- 2. Sutherland, D.E., et al., *Total pancreatectomy and islet autotransplantation for chronic pancreatitis*. J Am Coll Surg, 2012. **214**(4): p. 409-24; discussion 424-6.

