5.1 Study endpoints

- 5.1.1 Primary endpoints:
 - Quotient of MMTT stimulated (90min) C-peptide/glucose/IEQ/Kg at 6 and 12 months after TPAIT.

Rationale for the proposed endpoint: MMTT is a common metabolic test used to assess the insulin and C-peptide response to a mixed meal challenge. It triggers physiologic pathways to induce maximal insulin and C-peptide secretion. It is simple to conduct, and the outcome is widely believed to represent beta cell insulin secretion capacity. In recipients of islet allografts, the ratio of MMTT C-peptide/glucose at 90min correlates with the islet mass infused and it proves a valuable indicator of islet function. Whereas IVGTT

is also broadly utilized to assess islet function, our preference has been given to a test that shows correlation with predicted islet yield (used in a pre-randomization step) and infused islet mass.

5.1.2 Secondary endpoints:

- Stimulated C-peptide area under the curve (AUC) in response to MMTT at 6 and 12 months after TPAIT.
- Stimulated glucose AUC in response to MMTT at 6 and 12 months after TPAIT.
- Stimulated C-peptide and glucose levels in response to MMTT at 6 and 12 month after TPAIT.

5.1.3 Innovative endpoints:

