5.1.3.2 Part II: Genome-wide Gene Expression in TPAIT Patients

Differential gene expression calls will be done on isolated islets. These will be compared to appropriate control gene expression sets [52].

5.2 Study outcomes:

5.2.1 Primary outcomes:

- Increased quotient of stimulated C-peptide/glucose level normalized for IEQ/Kg infused in response to MMTT at 12 months in the HCQ-treated compared to placebo arm.

5.2.2 Secondary outcomes:

- Higher C-peptide AUC in response to MMTT 12 months in the HCQ-treated compared to placebo arm.
- Higher ratio of C-peptide AUC to glucose AUC in response to MMTT at 12 months in the HCQ-treated compared to placebo arm.

5.2.3 Innovative outcomes:

- Lower rates of oxygen consumption within isolated islets from CP patients compared to commercial controls
- Higher rates of oxygen consumption within isolated islets of HCQ-treated subjects compared to placebo.
- Full RNA sequence library for isolated islets from CP patients

5.3 Data collection:

The clinical data will be collected under auto islet registry stored in REDCap. All data in the Islet Isolation Laboratory at the Institute of Cellular Therapeutics, Allegheny Health Network and [name] Laboratory of the Cleveland Clinic Lerner Research Institute will be de-identified and collected into Microsoft Excel as medium, then transferred to REDCap by the investigators. All investigators will have received proper HIPPA training.

5.4 Data access and confidentiality:

All data will be collected either directly into REDCap or indirectly through Microsoft Excel on CCF Desktop computer as medium. The data will contain no personal health identifier (PHI) when it is being shared with investigators outside of the CCF. A study ID will be assigned to each subject. The deidentified clinical data will be shared for the purpose of manuscript construction under the standard user data agreement from the CCF IRB Committee. All investigators will have received proper HIPPA training.

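### The 75% power behind 5 per arm is calculated for plain CP/G, while the primary endpoint is CP/G normalised for IEQ/kg; a minor addition is to report the divisor by arm

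*Combined protocol and SAP*

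**What the plan says.** The primary endpoint in Section 5.1.1 is "Quotient of MMTT stimulated (90min) C-peptide/glucose/IEQ/Kg at 6 and 12 months after TPAIT". The primary outcome in Section 5.2.1 is "Increased quotient of stimulated C-peptide/glucose level normalized for IEQ/Kg infused in response to MMTT at 12 months", HCQ against placebo. The hypothesis in Section 5.5 is on the same scale: a higher CP/G on HCQ "compared to the placebo group, after normalization for IEQ/Kg infused".

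The sizing inputs in Section 5.5 are on another scale. The mean and SD are introduced as "We applied the proposed increments to estimate levels of the CP/G (0.35±0.07) based on our historical TPAIT data", and the assumed effect is one "which is equivalent to 0.08-0.12 CP/G difference and a 0.07 standard deviation". The infused mass enters only as a historical figure, "indicating on average IEQ/Kg infused of 4500±1000". On these inputs the plan settles on "a sample size of 10 subjects (5 for each arm) with the same assumptions but at 75% power". Table 3 uses the same units.

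On the divisor, patients are randomised before pancreatectomy (Section 4.2), start study drug 30 days before surgery (Sections 3.2 and 4.4), and have their islets counted at isolation (Section 4.1).

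**The concern.** Dividing CP/G by IEQ/kg gives a variable with a different spread. Its SD depends on how closely CP/G follows IEQ/kg. If they are weakly related, division adds noise and power falls. If they are strongly related, division removes noise and power rises. The plan gives neither the SD of the quotient nor the correlation, so the 75% offered in support of 5 per arm describes a variable that is not the primary endpoint.

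The second, smaller issue is that the divisor is itself measured after randomisation and on treatment. If the drug altered islet yield in either direction, the quotient and overall graft function could part company. The plan does not say how such a result would be read. The pre-surgery yield groups (Sections 3.1 and 4.2) balance a baseline prediction and do not address this.

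**Working it through.** **Inputs from Section 5.5.** CP/G 0.35, SD 0.07; IEQ/kg 4500, SD 1000; difference 0.08 to 0.12; one-sided two-sample t-test with equal variances; alpha 0.05; 5 per arm.

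**Step 1: the plan's own figure.** Power is the probability that a noncentral t with 2n − 2 degrees of freedom and noncentrality δ/(σ√(2/n)) exceeds the 5% critical value. For δ = 0.12, σ = 0.07 and n = 5, the noncentrality is 0.12/(0.07 × 0.632) = 2.71 and power is 79.6%. Five per arm is the smallest n with at least 75%. Six per arm gives 86.8% and is the smallest with at least 80%. All nine cells of Table 3 reproduce at 75% power, one-sided, in plain CP/G units. The two-sided test gives 6 per arm for 0.12 and the one-sided normal approximation gives 4, so the plan's calculation is identified as the un-normalised one.

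**Step 2: the difference.** For a mean of 0.35, 20% to 30% is 0.07 to 0.105. The stated 0.08 to 0.12 is 0.08/0.35 = 22.9% to 0.12/0.35 = 34.3%. The two ranges do not agree. At 30% (0.105), un-normalised power with 5 per arm is 69.8%, not 75%.

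**Step 3: the normalised quotient.** The coefficients of variation (CV) are 0.07/0.35 = 0.200 for CP/G and 1000/4500 = 0.222 for IEQ/kg. By the delta method, with correlation ρ between them,

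CV of quotient = √(0.200² + 0.222² − 2ρ × 0.200 × 0.222).

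At ρ = 0.5 this is √(0.0400 + 0.0494 − 0.0444) = 0.212. If the drug leaves IEQ/kg alone, a relative rise in CP/G is the same relative rise in the quotient, so the relative difference can be put into the same power formula.

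| Assumed ρ | CV of quotient | Power, 30% difference | Power, 34.3% difference (0.12) |
|---|---|---|---|
| 0 (lower bound) | 0.299 | 42.3% | 50.5% |
| 0.3 | 0.250 | 53.4% | 63.0% |
| 0.5 | 0.212 | 65.5% | 75.4% |
| 0.7 | 0.165 | 83.6% | 91.1% |
| 0.8 | 0.135 | 93.9% | 97.7% |
| Un-normalised CP/G | 0.200 | 69.8% | 79.6% |

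The quotient has the same CV as plain CP/G at ρ = 0.222/(2 × 0.200) = 0.556. It reaches 75% power at ρ of about 0.49 for a 34.3% difference and about 0.61 for 30%. A log-normal simulation agreed with these powers to within about 2.5 percentage points. Zero correlation is only a lower bound, because Section 3.2 calls infused mass the strongest predictor of function and Section 5.1.1 says "In recipients of islet allografts, the ratio of MMTT C-peptide/glucose at 90min correlates with the islet mass infused".

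**Step 4: the divisor.** The yield shifts here are illustrations and are not in the documents. If CP/G rose 34.3% and counted IEQ/kg rose 20%, the quotient would rise only 1.343/1.20 − 1 = 12%, with about 20% power at ρ = 0.5. If CP/G were unchanged and IEQ/kg were 20% lower, the quotient would rise 1/0.80 − 1 = 25%. A comparison of IEQ/kg between arms would settle little: the 95% confidence half-width is 2.306 × √(2/5) × 1000 = 1,458, or 32% of 4500. Two-sided power for a 20% shift is 24%.

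**The case against.** Section 5.5 does not rest 5 per arm on power alone. It also cites feasibility and the pilot nature of the trial, and Section 3.3 expects only 10 to 13 procedures a year. The section names the t-test for sample size only, so it states a hypothesis on the quotient without specifying its analysis test. The power may even be understated. The 0.35 ± 0.07 was estimated by applying islet-mass increments to historical data, and proportionality to IEQ/kg alone would give an SD of 0.35 × 1000/4500 = 0.078. Much of the 0.07 could therefore be spread that normalisation removes. All of this stands. It limits the consequence, but it does not supply a power for the primary endpoint.

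On the divisor, the plan's main mechanism is protection after infusion, for which function per infused islet is a coherent measure. Un-normalised C-peptide AUC, glucose AUC, stimulated levels and the AUC ratio are already secondary (Sections 5.1.2 and 5.2.2). That also stands and makes this a reporting matter. It is not empty, however: neither IEQ/kg by arm nor un-normalised 90-minute CP/G as a ratio is listed.

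A reader might infer that HCQ is likely to lower yield and so produce a spurious benefit. The documents do not support that. The background hypothesises that HCQ preserves islet mass, and Section 5.2.3 expects higher oxygen consumption in islets from HCQ patients. If anything, this points to a higher yield, in which case the quotient would understate a gain. No rate of misleading results can be given, because it depends on how CP/G responds to a change in yield. If CP/G moved in proportion to yield, the quotient would not shift at all.

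**Conclusion.** The first part holds as an error in the text: the 75% power and Table 3 belong to un-normalised CP/G and are not shown for the primary endpoint. Over assumed correlations of 0.3 to 0.8, power for the quotient runs from 53% to 94% at a 30% difference and from 63% to 98% at 0.12. It would be tempting to conclude that the trial is underpowered. The documents do not support this, because the direction of the error turns on a correlation that they do not give. The figures assume that correlation, approximate normality, no drug effect on IEQ/kg, and that 0.07 describes the spread of observed CP/G.

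The second part holds as a minor improvement. The divisor is measured on treatment, so a yield effect in either direction could separate the quotient from overall graft function. This is not a reason to abandon the quotient as primary endpoint.

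**What to change.** First reconcile the percentage and absolute differences in Section 5.5. Then add there:

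*The stated power and Table 3 apply to un-normalised CP/G only; power for the IEQ/kg-normalised primary endpoint depends on the correlation between CP/G and IEQ/kg.*

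Follow it with that power as a range over the assumed correlation, at the reconciled difference.

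In Sections 5.1.1, 5.2.1 and 5.5 add:

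*Un-normalised 90-minute CP/G and IEQ/kg infused will be reported by arm with confidence intervals beside the quotient. The quotient will be read as function per infused islet, and overall graft function will be read from un-normalised CP/G, whichever way the two differ. With 5 per arm, a non-significant IEQ/kg difference does not exclude a yield effect.*

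This needs no new data: islets are counted at isolation (Section 4.1), and C-peptide and glucose are measured at each MMTT (Section 4.5). Sample size and primary endpoint stay as they are. The cost is a little more reporting and a stated power that becomes a range.
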